#### 7.3. Statistical Analysis

The statistical analysis will follow the procedure outlined in ISO 80601-2-56:2017 section 201.102.

##### 7.3.1. Exclusion

Data from the following participants will be excluded from data analysis:

- Any subject administered antipyretic medications during study participation
- Any subject who does not complete at least one full round of measurements.
- Any subject whose data suggests a defective device or sensor.
- Any subject whose data suggests existence of external conditions that interfere with Rad-GT or reference measurements.

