## Clinical Performance of Masimo Rad-GT

### 1. OVERALL SYNOPSIS OF THE CLINICAL INVESTIGATION

Clinical investigation title:	Clinical Performance of Masimo Rad-GT
Study objective(s):	To validate the performance of Masimo Rad-GT.
Investigational device(s):	Masimo Rad-GT
Number of participants:	Approximately 73 subjects.
Inclusion criteria:	Refer to section 6.3.1
Exclusion criteria:	Refer to section 6.3.2
Duration of the clinical investigation:	The expected duration of study enrollment is 1 to 3 months.
Study endpoint(s):	Accuracy of temperature measurements using the Masimo Rad-GT will be compared to reference temperature measurements

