### 6. DESIGN OF THE CLINICAL INVESTIGATION

#### 6.1. General

This is a prospective, nonrandomized, single arm study. Temperature data will be obtained using the Masimo Rad-GT while obtaining [REDACTED] as a reference.

Accuracy of temperature measurements using the Masimo Rad-GT will be compared to the [REDACTED].

The validation of the accuracy of the temperature measurement in the investigational device may be determined using data collected from this study, in addition to data from other Masimo sponsored studies.

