#### Rad-GT Device Measurements:

\* Measurements may be taken several times throughout the study.

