### 8.3. Case Report Forms

The site shall capture study data in case report forms (CRFs) for each participant enrolled, to be provided to the sponsor. CRFs may be in paper or electronic format through electronic data capture (EDC) software. Masimo shall ensure that systems used for electronic CRFs are compliant with the requirements of 21 CFR Part 11 and ISO / IEC 27001 Certification. The CRFs will be completed and signed by the principal investigator or delegate. This also applies to those participants who fail to complete the study. If a participant withdraws from the study, the reason must be noted on the CRF. Case report forms are to be completed on an ongoing basis. CRF entries and corrections will only be performed by study site staff, authorized by the investigator. For paper CRFs, entries and corrections to the CRF will be made following Good Documentation Practices.

The CRF may include the following information, including but not limited to: inclusion / exclusion criteria, whether participant consent was obtained before start of study, demographic information, device readings, and if occurrence of any adverse event, protocol deviation, and device deficiencies, etc. The CRFs will be signed by the PI or delegate to attest that the data are complete and accurate.

CRF entries will be checked by the study monitor and any errors or inconsistencies will be queried to the site on an ongoing basis. Any changes made within an electronic CRF will be tracked by audit trail. Any changes on a paper CRF will be made directly on the CRF and will be initialed and dated by the person making the change. Query resolution will be assessed and confirmed by study monitor during site visit.

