*Note: Anticipated serious adverse device effect (ASADE) is an effect which by its nature, incidence, severity or outcome has been identified in the risk assessment.*

- **device deficiency**: inadequacy of a medical device with respect to its identity, quality, durability, reliability, usability, safety or performance

*Note 1: Device deficiencies include malfunctions, use errors, and inadequacy in the information supplied by the manufacturer including labelling.*

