### 14.4. Device Deficiencies Reporting

All Masimo device related deficiencies should be reported to the Sponsor and must be recorded in the CRF in a timely manner. When a Masimo device deficiency is observed, every effort should be made to return the device and its packaging to the Sponsor in a timely manner.

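### Section 7.3.1 lets a subject be excluded because the subject's own data suggest a fault or interference, so a large Rad-GT/reference difference can itself be the reason, and no analysis retaining these subjects is planned

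*Combined protocol and SAP*

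**What the plan says.** The synopsis (section 1) gives the endpoint: "Accuracy of temperature measurements using the Masimo Rad-GT will be compared to reference temperature measurements". Section 7.3.1 lists four grounds for removing a participant's data from the analysis. The first two are matters of fact: an antipyretic given during participation, and failure to complete one full round of measurements. The other two depend on what the data suggest:

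- The third ground concerns the equipment: "Any subject whose data suggests a defective device or sensor".
- The fourth ground concerns the surroundings: "Any subject whose data suggests existence of external conditions that interfere with Rad-GT or reference measurements".

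Removal is by whole participant, although section 6.4.3 says of the Rad-GT that "Measurements may be taken several times throughout the study".

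Other sections bear on the point:

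- Section 14.1 defines a device deficiency as "inadequacy of a medical device with respect to its identity, quality, durability, reliability, usability, safety or performance", and its second note extends this to the comparator.
- Section 14.4 says "All Masimo device related deficiencies should be reported to the Sponsor and must be recorded in the CRF in a timely manner".
- Section 8.3 allows deficiencies and protocol deviations to be entered on the CRF, and "CRF entries will be checked by the study monitor".
- Section 6.4.3 tells staff to keep the sensor's view clear and names examples of obstructions.

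Section 7.3 otherwise refers the analysis to section 201.102 of ISO 80601-2-56:2017.

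**The concern.** In an accuracy study, the sign in the data that most readily suggests a faulty sensor or a disturbed measurement is a large gap between device and reference. That gap is also the outcome. An exclusion rule that can be triggered by the outcome removes subjects in whom the device did badly along with subjects in whom something really went wrong, and nothing in the visible text separates the two.

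If exclusions fall on the largest differences, the reported spread is too small. The mean difference can also change. The visible plan does not call for analysis exclusions to be listed by reason, nor for a result with these subjects kept in, so a reader of the published accuracy could not judge what the exclusions did.

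**Working it through.** **Reading the rule against the rest of the plan**

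| Question | Visible text |
|---|---|
| Is evidence independent of the device/reference difference required? | Not in 7.3.1. Section 14.4 requires Masimo deficiencies to be recorded, but 7.3.1 does not make exclusion depend on that record. |
| Would a deficiency record separate a fault from poor accuracy? | Not by itself. The 14.1 definition includes inadequate performance, so a large error could qualify. |
| Are reference faults covered? | The 14.1 definition includes the comparator and 8.3 offers a place to record such faults. The recording duty in 14.4 names only Masimo devices. |
| Is external interference covered? | Section 6.4.3 names obstructions to avoid. No visible text ties an exclusion to a record of one. |
| Must exclusions be settled before differences are seen? | Not stated. |
| Is there an analysis with these subjects kept in? | None in the visible text. |

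**Inputs for the illustration**

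From the documents: up to 73 participants (section 7.2). That figure is attributed to the standard and cannot be reproduced, because the visible text gives no SD, margin, error rate or power. The point does not depend on it. The visible text also gives no number of expected exclusions, no error SD and no accuracy statistic, so the SD of the differences is used here as an assumed measure of spread.

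Assumed: k = 2, 4 or 7 subjects excluded, that is 2/73 = 2.7%, 4/73 = 5.5% or 7/73 = 9.6%. One difference d per subject, scaled to SD 1, either normal or t with 4 degrees of freedom. 40,000 simulated trials.

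**Effect on spread**

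Statistic: 1 − (mean SD after removing the k largest |d|) / (mean SD of all 73), with true bias zero.

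| | k = 2 | k = 4 | k = 7 |
|---|---|---|---|
| Exclusions unrelated to error | 0% | 0% | 0% |
| k most extreme, normal errors | 7.7% | 13.2% | 19.9% |
| k most extreme, t(4) errors | 16.6% | 24.1% | 32.0% |

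The effect is diluted in other settings (normal errors). With three readings per subject and half the variance between subjects, the falls are about 5%, 9% and 13%. If the 73 are pooled with 73 untouched subjects from elsewhere, they are about 4%, 6% and 9%.

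**Effect on the mean difference** (one normal difference per subject, k most extreme removed)

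- True bias zero: the absolute mean grew in about 52%, 48% and 40% of trials for k = 2, 4 and 7, so it can move either way.
- True bias 0.5 SD: it grew in about 12%, 3% and 1%, so it usually shrinks. The average mean falls from 0.50 SD to 0.45, 0.41 and 0.36 SD.

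**Cost of keeping an unproven faulty reading**

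Assume an SD of 0.25 °C without faults and j subjects of 73 each off by the same amount in the same direction:

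s² = 0.25² + [j(73 − j)/73] × off² / 72

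- No faults: 1.96 × 0.25 = 0.49 °C.
- j = 1, off = 1.0: s = 0.276, 1.96s = 0.54 °C.
- j = 3, off = 1.0: s = 0.320, 1.96s = 0.63 °C.
- j = 3, off = 1.7: s² = 0.0625 + (3 × 70/73) × 2.89/72 = 0.178, s = 0.422, 1.96s = 0.83 °C. The mean shifts by 3 × 1.7/73 = 0.07 °C.

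**The case against.** The strongest reply has four parts.

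*The plan already provides for faults.* Deficiencies of the device or the comparator fall within the definition, the CRF can hold them, a monitor checks the CRF, and obstructions to the sensor are named. All of this is true, and it means a record may well exist. What stands against it is that 7.3.1 does not require that record.

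*Data can be read more widely.* A subject's data include CRF entries and software output (section 8.1), so the rule could refer to a logged deficiency or an error state. That is a fair reading, but the wording does not confine the rule to it.

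*A criterion may sit out of view.* The standard is not reproduced, the measurement procedures in 6.4.3 are incomplete, and the acceptance table in 7.1 and its footnote are missing. This stands and limits the claim to the visible text. If a criterion exists, a cross-reference in 7.3.1 would settle the evidence question.

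*Removing faulty data is normal practice.* Agreed, and the proposed rule still does so.

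A reader might infer that the sponsor intends to trim poor readings, or that the plan has no safeguard against faulty measurements. The documents support neither inference. The wording permits selection on the outcome; it does not show that selection will occur.

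**Conclusion.** The point holds in a limited form. As written, the last two grounds in 7.3.1 permit exclusion on the accuracy outcome. Nothing in the visible text ties these exclusions to independent evidence, fixes when they are decided, or plans a result that retains the subjects. It should be fixed, with medium confidence because parts of the plan cannot be seen.

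The size is conditional. With 73 subjects, one difference each and the 2, 4 or 7 most extreme removed, the SD falls by about 8%, 13% or 20% with normal errors and about 17%, 24% or 32% with t(4) errors. The normal figures are therefore not a ceiling. Under either distribution this is the worst case for selection. Exclusions unrelated to error leave the SD unchanged on average.

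A reader might take these figures as a forecast, or conclude that exclusions would turn a failing device into a passing one. Neither follows. The documents give no exclusion count or error SD, the acceptance limits are not visible, and section 6.1 says the accuracy decision "may be determined using data collected from this study, in addition to data from other Masimo sponsored studies".

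**What to change.** 1. **Reword the last two grounds in 7.3.1.** Suggested text: *A subject is excluded for a fault or interference affecting the Rad-GT or the reference only if it is supported by evidence other than the size of the Rad-GT/reference difference: a CRF entry made at the time of measurement, a device check, or an error state or impossible value defined in advance. Exclusions are finalised and documented before any Rad-GT/reference difference or accuracy statistic is calculated.* The timing is set by calculation of the differences because both readings may come from one visit of about an hour and stand on the same CRF.
2. **List every exclusion by subject and reason.**
3. **Report one sensitivity analysis beside the main result.** It still applies the antipyretic and full-round exclusions but retains every subject excluded for a suspected fault or interference. It is not an acceptance gate.

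The cost is protocol wording, one list and one table, with no added subjects or procedures. The downside is that a faulty reading without independent evidence stays in the main analysis. In the most severe case worked above, three such subjects widen 1.96 SD from about 0.49 to 0.83 °C and shift the mean by about 0.07 °C. If the sponsor cannot accept that, parts 2 and 3 alone would still let a reader judge the effect of the exclusions.

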#### 7.4. Expected Dropout Rates

Participants may not complete the study for various reasons, at the investigator's or study staff's discretion, or because the participant does not want to continue the study. Due to the short duration and simple, noninvasive procedures of this study, there are limited expected dropouts.

### 8. DATA MANAGEMENT

#### 8.1. Data Management and Confidentiality

All documents associated with this protocol will be securely stored in a physical location or on password-protected computers. The confidentiality and retention of these documents will be protected to the extent provided and required by the law. All data will be de-identified before any statistical analysis. Only de-identified data will be shared with Masimo for research purposes stated in this protocol. Data collected by data capture software and data entered in case report form will be shared with Masimo via a secure, password-protected server that only study staff and Masimo study team members will have access to. Data will be retained for a minimum of 2 years following completion of the final analysis.

#### 8.2. Source Documents

Source data is all information, original records of clinical findings, observations, or other activities in a clinical trial necessary for the reconstruction and evaluation of the trial. Source data are contained in source documents. Examples of these original documents and data records include: hospital records, clinical and office charts, laboratory notes, memoranda, recorded data from automated instruments, and copies or transcriptions certified

# CLINICAL INVESTIGATION PLAN

## Clinical Performance of Masimo Rad-GT

after verification as being accurate and complete.

### 8.3. Case Report Forms

The site shall capture study data in case report forms (CRFs) for each participant enrolled, to be provided to the sponsor. CRFs may be in paper or electronic format through electronic data capture (EDC) software. Masimo shall ensure that systems used for electronic CRFs are compliant with the requirements of 21 CFR Part 11 and ISO / IEC 27001 Certification. The CRFs will be completed and signed by the principal investigator or delegate. This also applies to those participants who fail to complete the study. If a participant withdraws from the study, the reason must be noted on the CRF. Case report forms are to be completed on an ongoing basis. CRF entries and corrections will only be performed by study site staff, authorized by the investigator. For paper CRFs, entries and corrections to the CRF will be made following Good Documentation Practices.

The CRF may include the following information, including but not limited to: inclusion / exclusion criteria, whether participant consent was obtained before start of study, demographic information, device readings, and if occurrence of any adverse event, protocol deviation, and device deficiencies, etc. The CRFs will be signed by the PI or delegate to attest that the data are complete and accurate.

CRF entries will be checked by the study monitor and any errors or inconsistencies will be queried to the site on an ongoing basis. Any changes made within an electronic CRF will be tracked by audit trail. Any changes on a paper CRF will be made directly on the CRF and will be initialed and dated by the person making the change. Query resolution will be assessed and confirmed by study monitor during site visit.

### 8.4. Data Transfer and Storage

Original paper CRFs will be stored in a secure location at the site. Copy of the original paper CRFs may be scanned and sent to sponsor. If using electronic CRFs, the site staff will be assigned unique usernames and passwords for data security. Final copies of the electronic CRFs in EDC are stored on a secure server.

Only authorized sponsor personnel will have access to study data, and will move it to a secure and backed-up drive at Masimo.

CRFs will be checked for completeness and if there are inconsistent or missing data points, queries will be generated. If delegated study staff are to correct the paper CRF, they shall follow GDP practices to strike through old entry, add in new entry, and initial and date it, and provide the corrected information to sponsor. Corrections made to electronic CRFs will be tracked by audit trail and require PI or delegate sign-off.

### 8.5. Record Retention

Study data will be retained for the necessary period of time as required by the institution's regulations. Study records shall be retained for a minimum of two years after study closure. The Institution's own retention policies and regulations may apply in addition to the minimal requirement.

## 9. AMENDMENTS TO THE CLINICAL INVESTIGATION PLAN

Any changes made to the clinical investigational plan/study protocol will be documented by way of an amendment. Before submitting a protocol amendment to the IRB, the protocol amendment must be agreed upon and signed by both the principal investigator and the sponsor. The protocol amendment will be submitted to the IRB for approval. At a minimum, a redline version and a clean version of the new protocol amendment will be kept on file by the PI and the sponsor. Protocol amendments will need to be version controlled. Both PI and sponsor will retain the IRB approval letter as confirmation that the protocol amendment was approved.

## 10. DEVIATIONS FROM CLINICAL INVESTIGATION PLAN

Deviations from the protocol must receive both Sponsor and the investigator's IRB/ethics committee approval before they are initiated, with the exception that under emergency circumstances, deviations from the Clinical Investigation

# CLINICAL INVESTIGATION PLAN

## Clinical Performance of Masimo Rad-GT

Plan to protect the rights, safety and well-being of human subjects may proceed without prior approval of the sponsor or the IRB/ethics committee. Any protocol deviations initiated without Sponsor and the investigator's IRB/ethics committee approval that may affect the scientific soundness of the study, or affect the rights, safety, or welfare of study participants, must be documented and reported to the Sponsor and to the investigator's IRB/ethics committee as soon as a possible, but no later than 5 working days after the occurrence of the protocol deviation. In addition to documenting deviations on the CRF, the Protocol Deviation Form may also be used. If protocol deviations continue to occur frequently at a study site, a corrective and preventive action (CAPA) may be opened by the Sponsor.

**Withdrawal of IRB approval:** An investigator shall report to the sponsor a withdrawal of approval by the investigator's reviewing IRB as soon as possible, but no later than 5 working days of the IRB notification of withdrawal of approval.

## 11. DEVICE ACCOUNTABILITY

### 11.1. Receipt of Study Device

Upon receipt of the of the study device supplies, an inventory must be performed and the device accountability log filled out and signed by the person accepting the shipment. It is important that the designated study staff counts and verifies that the shipment contains all the items noted in the shipment inventory. Any damaged or unusable study devices in a given shipment will be documented in the study files. The investigator must notify the study sponsor of any damaged or unusable study devices that were supplied to the investigator's site.

### 11.2. Use of Study Device

Use of device will be documented on case report forms for each participant. Any unused devices must be returned to the Sponsor at the end of the study or before product expiration date.

### 11.3. Return or Destruction of Study Device

At the completion of the study, there will be a final reconciliation of study devices shipped, devices used, and devices remaining. This reconciliation will be logged on the device accountability log. Any discrepancies noted will be investigated, resolved, and documented prior to return or destruction of unused study devices. Devices destroyed on site will only be upon written instruction from the sponsor and will be documented in the study files. When a Masimo device deficiency is observed, every effort should be made to return the device and its packaging to the Sponsor in a timely manner.

## 12. STATEMENTS OF COMPLIANCE

This document is a clinical investigational plan for a human research study sponsored by Masimo Corporation. The study will be conducted in accordance with the ethical principles that have their origin in the Declaration of Helsinki. By participating in the study, the Investigator agrees to adhere to all stipulations of this protocol, the conditions of the Institutional Review Board (IRB) or Research Ethics Committee approval, federal and local regulatory requirements, 21 CFR 812, ISO-14155, International Conference on Harmonization Good Clinical Practice (ICH GCP) guidance.

The protocol, recruitment materials, and all participant materials will be submitted to the Institutional Review Board (IRB) for review and approval. Approval of both the protocol and the consent form must be obtained before any participant is enrolled. Any amendment to the protocol will require review and approval by the IRB before the changes are implemented to the study.

## 13. INFORMED CONSENT PROCESS

A waiver of formal, written informed consent is requested because this study involves minimal risks and does not adversely affect participant rights and welfare. An information sheet will be provided at the start of the study to inform the patient/LAR about the study and what data will be collected. Verbal consent will be collected prior to study procedures. Reasonable and appropriate protections will be implemented so that risks related to invasion of privacy and breach of confidentiality is no greater than minimal.

### 14. ADVERSE EVENTS, ADVERSE DEVICE EFFECTS, AND DEVICE DEFICIENCIES

#### 14.1. Definitions

The definitions for adverse event, adverse device effect, serious adverse event, serious health threat, serious adverse device effect, and unanticipated adverse device effect, device deficiencies are provided below (ISO 14155, 21 CFR 812.3(s)).

- **adverse event**: untoward medical occurrence, unintended disease or injury, or untoward clinical signs (including abnormal laboratory findings) in participants, users or other persons, whether or not related to the investigational medical device and whether anticipated or unanticipated (ISO 14155)
- **adverse device effect**: adverse event related to the use of an investigational medical device
- **serious adverse event**: adverse event that led to any of the following:
  - a) death
  - b) serious deterioration in the health of the participant, users, or other persons as defined by one or more of the following:
    - 1) a life-threatening illness or injury, or
    - 2) a permanent impairment of a body structure or a body function including chronic diseases, or
    - 3) in-patient or prolonged hospitalization, or
    - 4) medical or surgical intervention to prevent life-threatening illness or injury, or permanent impairment to a body structure or a body function,
  - c) fetal distress, fetal death, a congenital abnormality, or birth defect including physical or mental impairment

*Note: Planned hospitalization for a pre-existing condition, or a procedure required by the Clinical Investigation Plan, without serious deterioration in health, is not considered a serious adverse event.*

- **serious health threat**: signal from any adverse event or device deficiency that indicates an imminent risk of death or a serious deterioration in the health in participants, users or other persons, and that requires prompt remedial action for other participants, users or other persons.

*Note: This would include events that are of significant and unexpected nature such that they become alarming as a potential serious health hazard or possibility of multiple deaths occurring at short intervals.*

- **serious adverse device effect**: adverse device effect that has resulted in any of the consequences characteristic of a serious adverse event
- **unanticipated serious adverse device effect**: serious adverse device effect which by its nature, incidence, severity or outcome has not been identified in the current risk assessment

*Note: Anticipated serious adverse device effect (ASADE) is an effect which by its nature, incidence, severity or outcome has been identified in the risk assessment.*

- **device deficiency**: inadequacy of a medical device with respect to its identity, quality, durability, reliability, usability, safety or performance

*Note 1: Device deficiencies include malfunctions, use errors, and inadequacy in the information supplied by the manufacturer including labelling.*

